2.3 Safety Objective(s)

To document the number and severity of all adverse events that are causally related to the μ Cor system.

2.4 Additional Objective(s)

NA

3 Study Design

3.1 General Design

3.1.1 Study Description

Subjects meeting the inclusion/exclusion criteria will wear μ Cor for up to 90 days from the day of fitting. 500 total patients will be enrolled. There will be an interim analysis when the 200th subject has finished the study to assess for distribution of patients with reduced and preserved LVEF. The first 200 subjects enrolled in the US will exclusively wear the device in the side position. The subsequent subjects in the US will follow an alternating pattern of front position and side position placement.

Subjects will be fitted with μ Cor during discharge of a heart failure related hospitalization or within a clinic visit that has occurred within 10 days of a heart failure related hospitalization. The μ Cor fitting will mark day 0 of the study. An LVEF measurement will be recorded during enrollment or within 30 days post enrollment if an LVEF measurement has not been recorded within 30 days prior to enrollment. An investigator assessment will be performed during all clinic visits. The assessment template is shown in Appendix A.

Subjects will be given a diary at enrollment that will ask them to rate their degree of specific symptoms of heart failure such as shortness of breath and fatigue as well as mark any heart failure related clinical events or medication changes that have occurred since the last entry. The subject diary is shown in Appendix A.

Study follow up visits will occur at day 30, day 60, and day 90. There will be no follow up visit if the subject has stopped wearing the device. During follow up visits the subjects will be asked about any heart failure related clinical events or change in symptoms that have occurred since the last follow up. The subject will receive a study based weekly phone call asking the subject about any recent heart failure related clinical events or change in heart failure symptoms. During the weekly phone call the subject will be reminded to fill out the daily diary. No phone calls will be given on the week where there is a study follow up visit. There will be no follow up visit if the subject has stopped wearing the device. In case of adverse skin reaction to the μ Cor adhesive and/or electrodes, on the discretion of physician, subjects may discontinue wearing the device for

up to 48 hours. In the event the subject has stopped wearing the device completely, follow up phone calls will continue to be conducted per protocol in order to capture clinical information.

During the Day 90 visit, the subject will be given the option to continue wearing the μ Cor for an additional 90 days. Furthermore, if the subject experienced a heart failure related clinical event within the initial 90 days of wear, the subject will be given the option of wearing the μ Cor for 30 days following the heart failure event. If the subject chooses additional wear time, weekly phone calls and monthly visits will be structured identical to that of the main study period. The μ Cor will be returned at end of use.

There will be a follow up at six months and one year post enrollment to document mortality data, heart failure related clinical events, and health care utilization data. A timeline visualization of the study procedure is shown in Figure 7.

[figure not shown]

Figure 7: Procedure Flow of BMAD Study

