6.2 Scheduled Visits and Phone Calls

The scheduled visits are summarized in Table I and include the initial visit along with visits at day 30, 60, and 90. There will also be weekly phone calls to the patient. No monthly visits or weekly phone calls will occur if the subject has stopped wear. The phone calls will be conducted within no more than 2 days before or after the scheduled date. The scheduled visits will be conducted within no more than 5 days before or after the scheduled date. During the optional extended 90 day wear period, scheduled clinic visits and weekly phone calls will continue to take place following the procedures in Visits 2-4 with the exception of 6.2.4.6 (asking again for additional wear). Chart review and a follow up phone call will take place at 6 months and 1 year post enrollment.

6.2.1 Visit 1: Screening, enrollment and start (To occur during hospital discharge for decompensated heart failure or during a clinic visit in an out-patient setting no more than 10 days post hospital discharge).

6.2.1.1 All subjects will complete the Kansas City HF and study specific questionnaire.

6.2.1.2 A chart review will be used to evaluate patients for enrollment. A screening log will be maintained.

- 6.2.1.3 Patients meeting the initial Inclusion/Exclusion criteria will be approached for consenting.
- 6.2.1.4 The initial clinical and demographic data will be recorded in every subject. These may be done by chart review and will include:
- 6.2.1.5 Demographic characteristics, including gender, age, height and weight will be recorded.
- 6.2.1.6 Medical history will be recorded, including comorbidities, heart disease and physical disability.
- 6.2.1.7 Medical therapy for heart failure will be recorded for all subjects.
- 6.2.1.8 LVEF measurement within the past 30 days will be recorded if available. If a previous LVEF is not available, one will be obtained within 30 days of enrollment.
- 6.2.1.9 Subjects will be given a physical assessment.
- 6.2.1.10 Subjects will be assigned to wear the patch at either the front or side location (alternating 1:1)
- 6.2.1.11 Subjects will be fitted with μ Cor at hospital discharge or departure from clinic.
- 6.2.1.12 Device fitting will follow current Instructions for Use (IFU) procedures.
- 6.2.1.13 The date and time when μ Cor wear began will be recorded.
- 6.2.1.14 A clinic visit appointment will be scheduled to coincide with the end of the first 30 days of μ Cor wear.

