- 6.2.1.15 The subject's weight will be obtained.
- 6.2.1.16 The subject's previous 90 day hospital admission rate will be determined through chart review.

6.2.2 Visit 2: μ Cor Wear Day 30.

- 6.2.2.1 All subjects will complete the Kansas City HF and study specific questionnaire.
- 6.2.2.2 An in-center appointment will be scheduled to coincide with the end of 60 days of μ Cor wear.
- 6.2.2.3 All subjects will be asked about the following events since their last visit:
 - Any medication changes
 - Any physician visits, both planned and unplanned
 - Any hospitalization, including heart failure hospitalization
 - Any emergency room visits
 - Any symptoms, including syncope, dyspnea, palpitations and chest pain

6.2.2.4 A weight measurement will be obtained.

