6.4 Long-term Clinical Outcome Assessment

The subject will receive a follow up phone call 6 months and 1 year from the enrollment date to assess for mortality status, heart failure related clinical events that have occurred since the end of μ Cor wear, and any health care utilization that has occurred since the end of μ Cor wear. A chart review will be performed during both of these calls as well. Subjects will answer mailed heart failure questionnaires and mail the questionnaires back to the site.

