6.6 Weekly Phone Calls

There will be weekly phone calls to the subject to monitor changes in the health status of the subject. These calls will be performed by the site. The calls will reiterate the importance of completing the daily subject diary and document any health care usage by the subject. The calls will also document any heart failure related clinical events reported by the subject. No phone calls will occur if the subject has stopped wear.

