8.7 Futility Analysis

The study will be considered ineffective if the interim analysis determine the study will be unsuccessful enrolling the required number of subjects (≥ 1 subject per center-month), or if occurrence of the primary endpoint is deemed insufficient to successfully complete the study with the planned number of subjects.

Both an interim and futility analysis will be performed once the 200th subject has completed wear time. Primary and secondary endpoints will be assessed. With 200 patients completing wear time, it is expected that there would be about 25 -30 heart failure related clinical events. If during the interim and futility assessments, there are less than 5 heart failure events, a protocol change will be considered.

9 Health Economic Evaluation

The Kansas City Heart Failure Questionnaire will be given to the subjects at all monthly clinic visits. We will develop a model to examine the costs and benefits of using uCor. The model will use data from our review of monthly collected questionnaire, heart failure event, as well as data from recognized sources (e.g. national published data, finance department of hospital), and experts' advice

10 Safety and Adverse Device Effects

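### When a subject stops wear for good, the remaining Day 30/60/90 visits are cancelled, so the monthly questionnaire series increasingly describes continuing wearers only

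*Combined protocol and SAP*

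**What the plan says.** Section 3.1.1 states twice: "There will be no follow up visit if the subject has stopped wearing the device". Section 6.2 agrees as far as visits go: "No monthly visits or weekly phone calls will occur if the subject has stopped wear". Section 3.1.1 treats a skin-related pause of up to 48 hours separately from stopping completely, so the rule is about permanent stopping.

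The Visit 1 to 4 procedures in section 6.2 each contain the line "All subjects will complete the Kansas City HF and study specific questionnaire", together with weight and a physical assessment. Section 3.1.1 places the Appendix A congestion assessment at clinic visits. Section 9 ties the health-status measure to the same visits: "The Kansas City Heart Failure Questionnaire will be given to the subjects at all monthly clinic visits". It then names the monthly questionnaire as an input to the cost model.

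After the 90-day period, section 6.4 collects questionnaires without a clinic visit and without any condition on wear: "Subjects will answer mailed heart failure questionnaires and mail the questionnaires back to the site". Table 1 schedules questionnaires and weight at 6 months and 1 year, and physical assessment at Visits 1 to 4 only.

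On missing data, section 8.6.3.1 excludes any imputation. Section 8.6.3.2 drops a subject who is missing more than half of the data, without defining which data are counted.

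**The concern.** The rule makes the collection of health-status data depend on whether the device is still worn. Someone who stops on day 20 and remains in the study, reachable and willing, is not asked for another questionnaire until about day 180. Section 8.6.1 lists missed visits and loss to follow-up as sources of missing data, but not visits that the protocol itself cancels. Section 8.6.2.1 asks staff to make every effort to keep contact.

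The output at stake is the monthly questionnaire series, which feeds the section 9 model and the quality-adjusted life-year endpoint 3.3.6. At each successive visit it describes a group more strongly selected for continued wear. If stopping is related to health status, the summaries will not represent the enrolled population. No analysis can later restore answers that were never requested.

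**Working it through.** The plan gives no figure for visits lost through stopping wear, so there is nothing to reproduce. The check sets the rules against the schedule and then counts occasions.

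**Step 1. Is there another collection route before 6 months?**

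| Item | Scheduled at (sections 3.1.1, 6.2, 6.4, Table 1) | After a permanent stop |
|---|---|---|
| Questionnaires | Visits 1–4, 6 months, 1 year | none until 6 months |
| Weight | Visits 1–4, 6 months, 1 year | none until 6 months |
| Physical assessment and congestion score | Visits 1–4 | none |

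Weekly calls do not fill the gap. Section 3.1.1 says that after a complete stop "follow up phone calls will continue to be conducted per protocol in order to capture clinical information", whereas section 6.6 says "No phone calls will occur if the subject has stopped wear" and section 6.2 agrees with 6.6. These passages must be reconciled. Even if the calls continue, their described content is health-care use, heart failure events and symptom changes. It does not include the questionnaire, weight or congestion score.

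**Step 2. Occasions lost, by time of stopping.** There are 4 clinic occasions (Visits 1–4) and 6 questionnaire or weight occasions (those 4 plus 6 months and 1 year).

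| Permanent stop | Visits cancelled | Share of 4 clinic occasions | Share of 6 questionnaire occasions |
|---|---|---|---|
| before the Day 30 visit | 3 | 3/4 = 75% | 3/6 = 50% |
| between Day 30 and Day 60 | 2 | 2/4 = 50% | 2/6 = 33% |
| between Day 60 and Day 90 | 1 | 1/4 = 25% | 1/6 = 17% |

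The exclusion rule in 8.6.3.2 needs more than 50% missing. On these counts only a stop before Day 30, judged on clinic occasions, crosses it (75%). On questionnaire occasions the same subject sits at exactly 50% and is kept. Whether the rule removes such subjects depends on a definition that the plan does not give.

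**Step 3. How many subjects?** The only related figure is the wear time of over 70% anticipated in section 7.1. That is a share of time worn, not a rate of permanent stopping. With the study size of 500 (section 5.2) and an assumed proportion s stopping before Day 90, the number without Day 90 data is 500 × s:

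- s = 5%: 25
- s = 10%: 50
- s = 20%: 100
- s = 30%: 150

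**Step 4. Which endpoints are touched?** The primary objective (section 2.1) is evaluated during the wear period and relates device readings to events. After a permanent stop there are no readings to pair, so little is lost. The same holds for endpoint 3.3.2. Endpoint 3.3.6 and the section 9 model use the monthly questionnaire directly, so the gap falls there.

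**The case against.** The strongest defence is that this is a deliberate, repeated choice in an observational study of device readings, and that tying visits to wear suits that purpose. For the primary endpoint this stands. It is also fair that the line requiring all subjects to complete the questionnaire sits under visit headings and can mean those who attend. The argument therefore does not rest on a contradiction there. In addition, the cost model draws on heart failure events, published data and expert advice, so the questionnaire is only one of its inputs.

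Three stronger readings are tempting, and the documents do not support them.

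- *A reader might infer that these data exist only for subjects who tolerate the device.* They do not. Everyone has Visit 1, early stoppers keep the visits they attended, and questionnaires and weight are scheduled at 6 months and 1 year regardless of wear. Stopping may also have causes other than intolerance.
- *A reader might infer that Visit 4 is lost for completers seen late.* Section 6.2 says "The scheduled visits will be conducted within no more than 5 days before or after the scheduled date", so Visit 4 may fall on days 85 to 95, and 5 of those 11 days (45%) lie beyond the 90-day wear limit. But 6.2.4.1 makes discontinuation a Visit 4 procedure, 7.3.3 places device return at the final scheduled visit, and 3.1.1 offers continued wear during the Day 90 visit. The device is evidently expected to stay on until Visit 4. This is a wording matter, not a demonstrated loss.
- *A reader might infer that results will look too favourable, or that the symptom endpoint 3.3.3 is lost as well.* The documents do not link stopping to heart failure status. The foreseeable device effect they name is skin rash (10.1.1), and they offer 30 days of wear following a heart failure event. Symptoms are also recorded in the daily diary, which is not said to end with wear.

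**Conclusion.** The point holds in a limited form. Following the plan as written leaves wear-dependent gaps in the Day 30 to 90 questionnaires, weights and congestion scores of permanent stoppers: one to three visits each, depending on when they stop. The consequence is selection in one named secondary output, the questionnaire-based part of the cost model. The size is 25 to 150 subjects without Day 90 data if 5% to 30% stop. Those rates are assumptions, and the direction of any bias is unknown. The case for acting is that the gap is avoidable, cannot be repaired afterwards, and is cheap to close.

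**What to change.** Amend sections 3.1.1 and 6.2 so that subjects who have stopped wear but remain in the study still complete the remaining Day 30/60/90 heart failure questionnaires by the mail route of section 6.4. In the statistical plan and section 9, summarise the questionnaires for all enrolled subjects and separately by wear status at each time point, so that any selection is visible.

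In the same amendment, one clarifying sentence could say that the cancellation rule concerns stopping before the planned end of wear and does not remove Visit 4 for subjects who wore the device to Day 90.

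The cost is protocol wording plus at most three mailings per early stopper. On the assumed range, that is no more than 3 × 25 = 75 to 3 × 150 = 450 mailings over the study, with no new clinic visits or staff. The change does not recover the congestion score or physical assessment, and it adds no weight measurement. A separate chart review of events to Day 90 is not proposed, because the 6-month call and chart review in section 6.4 already cover events since the end of wear.

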3.1.2 Expected Duration of the Study

The anticipated enrollment period will be 1 year. The total anticipated study period will be 2.5 years.

3.2 Primary Study Endpoints

The primary endpoints that will be evaluated at the end of the study include:

3.2.1 Correlation of μ Cor readings (thoracic fluid index, cardiac rhythm, respiration rate, posture, and physical activity) to clinical events

3.3 Secondary Study Endpoints

The various secondary endpoints that will be evaluated during the entire study include:

- 3.3.1 Establishment of rate of occurrence of VT/VF episodes and arrhythmic death in patients.
- 3.3.2 Correlation between μ Cor measurements and patient reported symptoms
- 3.3.3 Frequency, timing, and severity of patient reported symptoms
- 3.3.4 Hospital readmission rate during the study period
- 3.3.5 Hospital readmission rate during previous 90 days prior to enrollment in study.
- 3.3.6 Cost-effectiveness data that supports a benefit in quality adjusted life years (QALY)
- 3.3.7 Mortality, heart failure related events, and health care utilization data at six months and one year post enrollment

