11.5	DATA SAFETY MONITORING BOARD (DSMB).....	19
12	DATA COLLECTION AND MANAGEMENT PLAN.....	19
12.1	DATA COLLECTION.....	19
12.2	DATA HANDLING AND RECORD KEEPING.....	19
12.3	DATA TRANSMISSION FROM SPONSOR.....	20
12.4	STUDY MONITORING PLAN.....	20
13	RISKS AND BENEFITS.....	20
14	ETHICAL CONSIDERATIONS.....	21
14.1	SUBJECT CONSENT AND CONFIDENTIALITY.....	21
14.2	SUBJECT FINANCIAL RESPONSIBILITY AND STIPENDS.....	21
15	PUBLICATION PLAN.....	21
16	INTELLECTUAL PROPERTY AND PATENTS.....	22
17	LIST OF ABBREVIATIONS.....	22
18	BIBLIOGRAPHY.....	23

Study Summary

Title	BENEFITS OF MICROCOR (μ Cor™) IN AMBULATORY DECOMPENSATED HEART FAILURE
Short Title	BMAD HF
ZOLL Protocol Number	90D0182
Study Design	Prospective and Observational Study
Study Duration	The study duration will last an estimated 2.5 years with 1 year estimated for enrollment
Study Center(s)	30 to 50 centers (Multinational)
Primary Objective(s)	To identify correlations between μ Cor measurements (thoracic fluid index, respiration rate, cardiac rhythm, physical activity, and posture) with occurrences of heart failure related clinical events within 90 days of hospital discharge for acute decompensated heart failure.
Study Population	Subjects hospitalized for acute decompensated heart failure or subjects presenting to an outpatient clinic within 10 days post-hospital discharge for heart failure. All subjects require an additional heart failure event within the previous 6 months.
Intervention	
Subjects meeting the inclusion/exclusion criteria will wear the μCor for up to 90 days.
 
During the study, clinic follow up will occur every 30 days. For all subjects, each scheduled clinic visit will include assessment of cardiac symptoms and any relevant clinically actionable events.
 
The subject will be given a daily diary to track symptoms, unplanned hospital visits, medication changes, and all other heart failure related clinical events.
 
Weekly phone calls to the subject will be given throughout the duration of the study to remind the patient to use the subject diary and to collect and record heart failure related clinical events.
 
Subjects will be contacted six months and one year from initial enrollment to assess the vital status of the subject, any heart failure related clinical events since the end of μCor wear, and any health care utilization since the end of μCor wear.

Study Size	A total of 500 subjects
Reference therapy	NA

1 Introduction

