6.7 Blinding and Unblinding of Study

During the study, physicians and subjects will be blinded to all μ Cor data. If the sponsor observes a potentially life threatening arrhythmia, the site will be notified.

7 Study Device Management

The μ Cor device log will be managed by the sponsor. The sites will keep a device log of all available μ Cor devices and make necessary requests to the sponsor when inventory is low. The study site will collect the device when the patient has ended wear. All used and unused devices will be returned to the sponsor when the study is completed. The investigator will be responsible for subject device accountability.

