12.4 Study Monitoring Plan

Monitoring activities will be conducted according to the Sponsor's standard operating procedure.

13 Risks and Benefits

µCor is a noninvasive medical monitoring device. Common risks associated with devices using medical adhesives include but are not limited to discomfort, skin irritation, itching, rash, contact dermatitis, or breaching of skin if the patch adhesive is the removed too quickly.

No study specific benefits to participation are anticipated.

14 Ethical Considerations

This study is to be conducted according to US and international standards of Good Clinical Practice (FDA Title 21 part 312 and International Conference on Harmonization guidelines), applicable local government regulations.

This protocol and any subsequent amendments will be submitted to a properly constituted Ethics Committee (EC) or Institutional Review Board (IRB), in agreement with local regulations, for formal approval of the study conduct. The decision of the EC/IRB concerning the conduct of the study will be made in writing to the investigator and a copy of this decision will be provided to the sponsor before commencement of this study. The investigator will provide a list of EC/IRB members and their affiliate to the sponsor.

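### Secondary endpoint 3.3.6 presupposes a QALY benefit that the study's own data cannot estimate

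*Combined protocol and SAP*

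**What the plan says.** Section 3.3 lists seven secondary endpoints. Six name a rate, a correlation or a set of data. The remaining one, 3.3.6, is "Cost-effectiveness data that supports a benefit in quality adjusted life years (QALY".

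The design is set out as follows:

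- The Study Summary calls the study a "Prospective and Observational Study" and enters NA in the row "Reference therapy".
- Section 3.1.1: "Subjects meeting the inclusion/exclusion criteria will wear" the device, and "500 total patients will be enrolled". Section 8.2 allocates patch position (front or side) and nothing else.
- Section 6.7: "During the study, physicians and subjects will be blinded to all" device data. The next sentence makes one exception: the sponsor notifies the site if it sees a potentially life threatening arrhythmia.
- Section 9: "We will develop a model to examine the costs and benefits of using uCor". Its inputs are the questionnaires, heart failure events, published and hospital finance data, and expert advice. It names no comparator strategy, source for a device effect, conversion to utilities, time horizon or sensitivity analysis.
- Section 8.4 plans descriptive statistics and qualitative analysis for all endpoints. Section 2.2 contains no objective on QALYs or cost-effectiveness; the nearest, 2.2.5, covers mortality, cause of death and utilization.

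**The concern.** An endpoint should be able to come out either way. As worded, 3.3.6 has no place for a neutral or unfavourable result.

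The design also offers nothing from which a benefit could be estimated. A QALY gain from a monitoring device is a difference between two strategies: care guided by the readings, and care without them. This study observes neither the second strategy in a separate group nor, apart from the arrhythmia notification, the first.

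At stake is what the study may claim. Two uncontrolled contrasts lie close to hand and could slip into the model as if they were the device effect. One is the change in questionnaire score from a baseline taken at, or within 10 days of, discharge. The other is the admission rate during the study (3.3.4) set beside the rate in the 90 days before enrollment (3.3.5). Recovery, concurrent treatment and selection can move both without any device effect.

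**Working it through.** The plan gives no effect size, precision or power for 3.3.6, so there is no figure to reproduce. The check is whether the quantity can be identified.

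**1. Within-study contrast**

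Incremental effect = mean QALY with device − mean QALY without device.

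Standard error = sd × √(1/n₁ + 1/n₀).

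Inputs: n₁ = 500 (Sections 3.1.1 and 5.2); n₀ = 0 (all subjects wear the device; reference therapy is NA).

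Result: √(1/500 + 1/0) is undefined, whatever the sd. Front versus side position compares device with device, so it does not help. Nor would a device-free group be enough on its own: with readings blinded, the contrast would show the effect of wearing the device, not of acting on its data.

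**2. What a model could take from the study**

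Section 9 gives no model structure. For illustration, take a simple product (my assumption):

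gain = (event rate) × (share of events signalled by the readings) × (share of signalled events averted by acting) × (QALY loss per event)

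| Factor | Can the study inform it? |
|---|---|
| Event rate | Yes: heart failure events, admissions, follow-up at 6 months and 1 year |
| Share signalled | In part: the primary endpoint relates readings to events |
| Share averted by acting on readings | No: readings are withheld from care and there is no comparator |
| QALY loss per event | In part: mortality and questionnaire scores, once a utility derivation is stated |

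The third factor decides whether there is any gain. Set it to zero and the product is zero, whatever the study finds on the others.

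**3. The before-and-after substitute under no device effect**

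This concerns admissions, not QALYs. It is shown only because such a contrast could be entered in a cost model.

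Assumptions: the index stay counts in the prior 90 days (the documents do not say), so the prior rate is at least 1.0 per subject; the event hazard is constant; and the Section 8.1 figure of 20% in 30 days, stated for heart failure events in patients with reduced LVEF, stands in for admissions in everyone.

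Expected events per subject in 90 days = −3 × ln(1 − p₃₀).

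At p₃₀ = 0.20: −3 × ln(0.80) = 0.67. Apparent fall from 1.0: 1 − 0.67 = 33%.

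| Assumed 30-day rate | Expected events in 90 days | Apparent change from 1.0 |
|---|---|---|
| 10% | 0.32 | 68% fall |
| 15% | 0.49 | 51% fall |
| 20% | 0.67 | 33% fall |
| 25% | 0.86 | 14% fall |
| 30% | 1.07 | 7% rise |

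The size and even the direction depend on the assumed rate. The true device effect is zero in every row, so the comparison cannot serve as the device effect.

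**4. Questionnaire change**

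The baseline is at or shortly after an acute admission, and Sections 3.1.1 and 6.2 end clinic visits once wear stops. Scores from the day 30, 60 and 90 visits therefore come from continuing wearers, with no group to show what would have happened otherwise.

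**The case against.** The strongest reply is that Section 9 plans a model, not a within-study comparison. Modelling is a usual way to examine a monitoring device before a controlled trial, and the study does supply real inputs. The endpoint is secondary, descriptive and untested, and no section says that score change or the prior 90-day rate will be read as a device effect. All of this stands. It limits the consequence, but it does not give 3.3.6 a quantity that can be estimated, and Section 9 still leaves the decisive input without a source.

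Four stronger readings are tempting, and the documents do not support them:

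- *Nobody acts on device data.* Section 6.7 provides for notifying the site of a potentially life threatening arrhythmia. This path is narrow and uncontrolled, so it does not rescue the endpoint, but it exists.
- *Any modelled gain would come wholly from outside.* Event rates, utilization, mortality and questionnaire scores would come from the study. Only the effect of acting on readings must be external.
- *Section 13 contradicts the endpoint.* Its statement "No study specific benefits to participation are anticipated" concerns people taking part in a study with blinded readings. It says nothing about later, unblinded use.
- *The Kansas City questionnaire is the only quality-of-life source.* Section 6.2 also gives a study specific questionnaire at each visit. Its content is not shown, so it cannot be ruled out as a source. What can be said is that no conversion to utilities is described.

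**Conclusion.** The concern holds in this form: 3.3.6 presupposes its result, and the study's own data cannot estimate an incremental QALY effect. The device versus no-device split is 500 to 0, and care is blinded to the readings apart from the arrhythmia notification. This conclusion rests on the stated design alone and needs no numerical assumption. A model may still project a gain, but its sign and size would depend on an outside assumption about acting on device data, which Section 9 does not name.

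The before-and-after figures (from a 68% fall to a 7% rise with no device effect) are illustrations under the stated assumptions. They show why that contrast must not be used; they are not evidence that the sponsor intends to use it. The primary endpoint is unaffected.

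**What to change.** Replace 3.3.6 with neutral wording, for example: *description of health status scores, heart failure events, mortality, resource use and costs over 90 days, 6 months and 1 year, as inputs to an economic model.*

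Add to Section 9:

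1. The study itself does not estimate a device effect on QALYs or cost-effectiveness.
2. Neither uncontrolled change in questionnaire scores nor a comparison with the prior 90-day admission rate will be used as the device effect.
3. Any modelled gain rests on a named external effect of acting on device data, reported with sensitivity ranges.
4. The comparator strategy and the derivation of utilities from the questionnaires are stated, together with the time horizon.

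The cost is a change to one endpoint and one section, with no change to visits or sample size. The sponsor gives up a claim of QALY benefit from this study, but keeps the data needed for a properly labelled model.
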